6.1 Sample Size Determination

Data for power analysis based on pilot study data (IRB# 19-011419). Power analysis is based on improvement in antibiotic stewardship with the following assumptions:

- Treatment groups are random and independent
- Microbial detection positivity rate using standard cultures = 54%
- Microbial detection positivity rate using nanopore sequencing = 77%

Analytical method:

- Sample size per group = 66 (total N = 132), Target size=70 per arm, total N=140
- Power = 80%, alpha (type I error) = 0.05, beta (type II error) = 0.2

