1.4 Clinical Data to Date

This study will use data that has been collected under the following research study: "Comparative Analysis of Bile Microorganisms in Patients Undergoing Major Hepatobiliary Operations", IRB# 19-011419 and published in two peer-reviewed journals^{44,48}. In brief, these studies involved analysis of intraoperative bile aspirate samples collected from 42 patients undergoing pancreatic head resection (total pancreatectomy, n = 9; pancreaticoduodenectomy, n = 33) at Mayo Clinic, Rochester (see Table 1 for patient characteristics). Metagenomic ONT sequencing was performed on bile aspirates to identify microbial species (bacterial, fungal) and antibiotic resistance genes. Sequencing results were then compared to bile cultures performed as part of Mayo Clinic's standard of care clinical practice to determine how ONT sequencing compared to current 'Gold Standard' culture practices^{44,48}.

To determine the optimum ONT protocol for detection of microbial species and antibiotic resistance genes present in the bile aspirates, different methods of DNA extraction, use of host DNA depletion, and use of different AMR gene databases were evaluated⁴⁸. In total, intraoperative biliary microbes were detected in 54.7% (23/42) of patients undergoing total pancreatectomy or pancreaticoduodenectomy using SC techniques. This included 35.7% (15/42) of patients with positive bacterial cultures, 2.4% (1/42) of patients with positive fungal cultures, and 16.7% of patients with positive fungal and bacterial cultures. The male sex, use of biliary instrumentation, and performance of vascular reconstruction during surgery was significantly correlated with the detection of biliary microbes.

Table 1: Clinical characteristics of patients included in our preliminary study

Clinical feature	Total	Biliary microbes ⁺	Biliary microbes ⁻	P value
Age, mean (IQR)	61 (22 - 71)	66.3 (46.3 - 81.3)	58.0 (18 - 82.6)	0.0858
BMI, mean (IQR)	26.4 (19 - 40.4)	26.3 (19 - 40.4)	26.4 (19.7 - 36.2)	0.9295
Sex, % male (n)	54.8 (23)	38.1 (16)	16.7 (7)	0.0375
Surgery indication, % (n)				0.892
Pancreatic ductal adenocarcinoma	45 (29)	50 (21)	19.0 (8)	
Intraductal Papillary Mucinous Neoplasm	7.1 (3)	0 (0)	7.1 (3)	
Neuroendocrine tumors	11.9 (5)	2.4 (1)	9.5 (4)	
Other	11.9 (5)	2.4 (1)	9.5 (4)	
ASM Score, mean (IQR)	2.6 (1 - 4)	2.7 (2 - 4)	2.5 (1 - 3)	0.1874
Type of surgery				0.9716
Total pancreatectomy, % (n)	21 (9)	11.9 (5)	9.5 (4)	

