2.2 Primary Objective

To improve antibiotic stewardship (reducing duration of peri-operative prophylactic antibiotic regimen, reducing administration of broad-spectrum antibiotic) by providing surgical team with rapid ONT sequencing data in the early post-operative setting.

Success Criteria: Significantly reduced antibiotic regimen duration and use of broad-spectrum antibiotics, corrected for key co-variates ($p<0.1$).

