2.2 Primary Study Endpoints

- Reduced administration of antibiotics with a non-significant ($p>0.05$) effect on SSI rate

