5.3 Follow up Data Collection

Outcomes will be abstracted from the medical record for 90-days post-operatively and will include outcomes of primary endpoints that include: duration of perioperative antibiotic regimen, total number of antibiotics administered, and administration of broad-spectrum antibiotics vs narrow-spectrum antibiotics. Secondary endpoints will include SSI rate, SSI severity (superficial, deep, organ/space, bloodstream, or urine), and total hospital costs. Standard post-pancreatectomy surgical outcomes will also be collected including: total hospital length of stay (days), ICU length of stay (days), need for and type of interventional procedures, pancreas-specific complications (pancreatic leak/grade, delayed gastric emptying, and post pancreatectomy hemorrhage) hospital readmission, and death. In addition, all culture results and ONT sequencing results will be captured and compared. Additional clinical data will be gathered if deemed appropriate for outcome analysis. Patients will be assigned a study identification number at the beginning of the study to aide in securing identifiable patient information. All patient information will be stored in a secure Medidata Rave database that

will be accessed by designated study members only. Statistical analysis will be performed to compare outcomes between study arms as described in analysis section of this application.

6 Statistical Plan

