6.2 Statistical Methods

Descriptive Statistics

The primary analysis of this study will be a modified intention to treat analysis (ITT), performed to determine how use of ONT changed patient treatment, i.e. did use of ONT improve antibiotic stewardship. Proportions of patients with detection of microbes of interest will be estimated along with exact 95% binomial confidence intervals. Comparisons of the proportions between the two study arms will be compared using Fisher's exact test or Chi-square test as appropriate. We will calculate the time from randomization to first microbial detection within a patient. We will report the mean difference in time to first microbial detection within 96 hours post randomization in both treatment arms, together with a 95% confidence interval. Comparison of time to first microbial detection within 96 hours post randomization, will be performed using Wilcoxon rank sum test or two sample t-test as appropriate. If there are any baseline imbalances in demographic or clinical variables between the two groups, we will perform the analysis using univariable and multivariable linear regression adjusting for these variables with imbalances as possible confounders. Duration of antibiotics, total number of different antibiotics, and broad-spectrum antibiotics vs narrow-spectrum antibiotics administered in the two arms will be compared to determine if use of ONT improved antibiotic stewardship by significantly reducing the duration of perioperative antibiotics and use of broad-spectrum antibiotics

Secondary analysis will evaluate SSI's will be evaluated and classified using ACS NSQIP definitions and data collected will include mortality rate, SSI incidence rate, ICU length of stay, total length of hospital stay, need for interventional procedures, and hospital readmission. Statistical analysis will be performed by the study team to determine if use of ONT significantly improved patient outcome compared to patients who received standard of care

only. The secondary endpoint of the study is a binary endpoint i.e. whether patients develop SSI (yes, no). Association between the secondary outcome and predictor variables will be assessed using univariable and multivariable logistic regression.

In both primary and secondary analysis, the following variables will be assessed for inclusion in the regression models

- Age at time of surgery DOB
- BMI at time of surgery RAVE calculate
- Sex

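### Section 6.1 attributes its 80% power to antibiotic stewardship, but 66 per arm is the sample size for a 54% vs 77% detection comparison; no power is given for the antibiotic endpoints, and the 77% cannot be traced to the pilot results reported

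*Combined protocol and SAP*

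**What the plan says.** Section 6.1 introduces the calculation with "Power analysis is based on improvement in antibiotic stewardship with the following assumptions". It credits the data to the pilot study and lists random independent groups, a culture positivity of 54%, and "Microbial detection positivity rate using nanopore sequencing = 77" per cent. From these it takes 66 per arm (132 in total) at 80% power and alpha 0.05, with a target of 70 per arm (140).

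The outcomes that define success are different:

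- Primary Objective, success criterion: "Significantly reduced antibiotic regimen duration and use of broad-spectrum antibiotics", adjusted for covariates, at p<0.1.
- Primary Study Endpoints: "Reduced administration of antibiotics with a non-significant" effect on SSI rate.
- Section 5.3: "outcomes of primary endpoints that include: duration of perioperative antibiotic regimen", together with the number of antibiotics and broad versus narrow spectrum.

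Detection does have a place in the analysis. In the paragraph on the primary analysis, 6.2 says "Proportions of patients with detection of microbes of interest will be estimated", and then "Comparisons of the proportions between the two study arms will be compared using Fisher's exact test or Chi-square test as appropriate".

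**The concern.** A reader will take N=140 as giving 80% power for the stewardship endpoints. The document does not show that. A detection rate describes what the laboratory finds; the primary endpoints describe how much antibiotic the patient receives, for how long, and how broad.

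For duration the link may even run the other way. Under General Design and Table 5, a negative ONT result is what triggers discontinuation at 24 hours, so a higher ONT positivity rate means fewer early stops. Detection could still help the spectrum component, because Table 5 narrows therapy on a positive result. It also allows stopping when the organisms found are judged clinically insignificant. So detection power cannot be read as power for duration.

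The 77% is also the only input that creates the difference being powered. If it cannot be sourced, the stated basis for 66 per arm goes with it.

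**Working it through.** **1. Reproducing the stated size.** Inputs from 6.1: p1 = 0.54, p2 = 0.77, alpha 0.05, power 0.80; 1:1 allocation from 5.2. Sidedness is not stated.

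n = [z(0.975)·√(2p̄(1−p̄)) + z(0.80)·√(p1(1−p1) + p2(1−p2))]² / (p2−p1)²

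- p̄ = 0.655, so 2p̄(1−p̄) = 0.45195; p1(1−p1) + p2(1−p2) = 0.2484 + 0.1771 = 0.4255.
- n = (1.3176 + 0.5490)² / 0.0529 = 3.4843 / 0.0529 = 65.9, i.e. **66 per arm**, as stated.
- Alternatives: one-sided 52; two-sided with continuity correction 75; unpooled 64; arcsine 66.
- Power at 70 per arm: 82.4% by the normal formula, 82.7% by exact enumeration of the uncorrected chi-square test.

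The arithmetic is right. What it powers is detection.

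**2. Inputs for the antibiotic endpoints.** The Primary Objective, Primary Study Endpoints, 5.3, 6.1 and 6.2 contain no SD, control rate, target difference or power for duration, number or spectrum. Power for these endpoints cannot be computed from the text.

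**3. Tracing the 77%.** Section 1.4 supports the 54%: "intraoperative biliary microbes were detected in 54.7% (23/42) of patients" by culture (23/42 = 54.8%). As an ONT positivity rate, 77% appears only in 6.1.

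- It is not a whole count out of 42: 32/42 = 76.2%, 33/42 = 78.6%.
- The nearest pilot figures in 1.4 (75%, 76%, 76.5%) are agreement with culture by species or genus, not positivity rates.
- Section 1.4 says ONT identified all contaminated cases, and 1.1 says it agreed perfectly when culture was negative. Read as any-organism positivity per patient, these imply 23/42, about 55%. On that reading 77% would need 0.77 × 42 − 23 = 9.3 of the 19 culture-negative patients to be ONT-positive.

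This is an inference. Section 6.1 states neither unit nor denominator, and others may have been meant.

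**4. Direction for duration.** Expected ONT-negative patients in Arm 2: 70 × 0.23 = 16.1 at 77% positivity, against 70 × 19/42 = 31.7 on the reading in step 3.

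**5. What 70 per arm detects with 80% power.**

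- Duration, two-sample t-test, 138 df: 0.477 SD at two-sided 0.05 and 0.422 SD at 0.10. The normal approximation (z(1−α/2) + z(0.80))·√(2/70) gives 0.474 and 0.420. For an assumed SD of 2 to 5 days: 0.477 × 2 = 0.95 to 0.477 × 5 = 2.4 days at 0.05; 0.84 to 2.1 days at 0.10.
- Broad-spectrum use, two proportions, at 0.05: a drop of about 18 points from an assumed control rate of 90%, and about 23 points from 75%, 60% or 50%.

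**6. Illustration only: duration power under assumed fixed courses.** Control: 54% at 10 days, 46% at 5 days (mean 7.70, SD 2.49). Arm 2: ONT-negative at 1 day, culture-positive at 10 days, and an assumed course for ONT-positive/culture-negative patients. No other variation. SE = √((SD₁² + SD₂²)/70); power from the non-central t.

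| ONT positivity | Course if ONT+/culture− | Difference (days) | Power, 0.05 | Power, 0.10 |
|---|---|---|---|---|
| 54%, same patients as culture | none | −1.84 | 85% | 91% |
| 77% | 5 days | −0.92 | 40% | 52% |
| 77% | 7 days | −0.46 | 14% | 22% |
| 77% | 10 days | +0.23 | wrong direction | wrong direction |

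The spread comes from the assumptions; it neither bounds nor estimates this trial's power.

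**The case against.** The strongest defence has four parts.

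- **Detection belongs to the primary analysis.** Section 6.2 places the between-arm detection comparison in that paragraph, beside the question of whether ONT improved stewardship, so N does match a planned comparison. This stands, and it makes 66 per arm a legitimate detection sample size. It does not turn detection into one of the endpoints named in the Primary Objective, Primary Study Endpoints or 5.3.
- **The source is stated.** Section 6.1 opens by crediting the pilot. This also stands, so it would be wrong to say the 77% has no stated source. What is missing is a definition, and a match to the results reported from that pilot. The full pilot results lie in cited papers that are not reproduced in the protocol.
- **The trial is labelled a pilot.** A pilot need not power every stewardship component. But this one makes a formal 80% power claim and sets significance-based success criteria, so the claim should be attached to the right quantity.
- **The trial may be adequately powered anyway.** On the pilot-implied reading with 5- and 10-day control courses, the fixed-course model gives about 84% power for duration at 0.05 and 90% at 0.10, using 23/42 in place of 54%. This is fair, and it is why no shortfall is claimed.

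**Conclusion.** Wrong as written. The 80% power in 6.1 belongs to a 54% vs 77% detection comparison and is attributed to antibiotic stewardship, for which the document gives no power. The reproduction of 66 per arm needs only the inputs in 6.1 and a two-sided test. The detectable differences for duration and spectrum need the assumed SDs and control rates shown.

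A reader might infer two stronger things, and the documents support neither:

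- **That the trial is underpowered for stewardship.** With no SD, rate or target difference given, power is indeterminate. Under assumed courses it can be adequate, low or in the wrong direction.
- **That the true ONT rate is about 55%, so there is no detection difference to find.** That holds only if the 77% means any-organism positivity per patient in the 42 reported patients. The conflict with 1.1 and 1.4 is real on that reading, but the reading is not confirmed.

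**What to change.** Keep N=140 and rewrite 6.1:

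1. Remove the attribution to stewardship. State that 66 per arm and 80% power apply only to the detection comparison in 6.2, with the uncorrected chi-square test.
2. Give the unit, denominator and source of the 77% and reconcile it with 1.1 and 1.4, or withdraw the 80% figure.
3. State what 70 per arm detects for duration with 80% power: about 0.48 SD at two-sided 0.05 or 0.42 SD at 0.10, with the SD assumption in days. For broad-spectrum use, give the detectable drop under a stated control rate, or say that it is not powered.
4. Base these figures on the alpha that defines success, after reconciling 0.05 in 6.1 with p<0.1 in the Primary Objective.

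If the sponsor prefers conditional power for duration, the assumed courses must be listed. First, the sponsor has to reconcile the statements on course length (1.1, General Design) and on whether ONT or culture guides therapy (1.5.2 with Table 3, General Design with Table 5). No clinical rule is proposed here.

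The cost is a rewritten section. If the 77% is kept as patient-level positivity, the concordance statements in 1.1 and 1.4 also need correcting. If it is withdrawn, the sponsor gives up the 80% statement and justifies N=140 by the detectable differences.

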6.2 Statistical Methods

Descriptive Statistics

The primary analysis of this study will be a modified intention to treat analysis (ITT), performed to determine how use of ONT changed patient treatment, i.e. did use of ONT improve antibiotic stewardship. Proportions of patients with detection of microbes of interest will be estimated along with exact 95% binomial confidence intervals. Comparisons of the proportions between the two study arms will be compared using Fisher's exact test or Chi-square test as appropriate. We will calculate the time from randomization to first microbial detection within a patient. We will report the mean difference in time to first microbial detection within 96 hours post randomization in both treatment arms, together with a 95% confidence interval. Comparison of time to first microbial detection within 96 hours post randomization, will be performed using Wilcoxon rank sum test or two sample t-test as appropriate. If there are any baseline imbalances in demographic or clinical variables between the two groups, we will perform the analysis using univariable and multivariable linear regression adjusting for these variables with imbalances as possible confounders. Duration of antibiotics, total number of different antibiotics, and broad-spectrum antibiotics vs narrow-spectrum antibiotics administered in the two arms will be compared to determine if use of ONT improved antibiotic stewardship by significantly reducing the duration of perioperative antibiotics and use of broad-spectrum antibiotics

Secondary analysis will evaluate SSI's will be evaluated and classified using ACS NSQIP definitions and data collected will include mortality rate, SSI incidence rate, ICU length of stay, total length of hospital stay, need for interventional procedures, and hospital readmission. Statistical analysis will be performed by the study team to determine if use of ONT significantly improved patient outcome compared to patients who received standard of care

only. The secondary endpoint of the study is a binary endpoint i.e. whether patients develop SSI (yes, no). Association between the secondary outcome and predictor variables will be assessed using univariable and multivariable logistic regression.

In both primary and secondary analysis, the following variables will be assessed for inclusion in the regression models

- Age at time of surgery DOB
- BMI at time of surgery RAVE calculate
- Sex
- Diabetes mellitus co-morbidity at time of surgery (clarifications needed for data collection)
- Cancer diagnosis
- ASA score at time of surgery
- Administration of chemotherapy prior to surgery (from what timepoint or date of last chemo?)
- Presence of biliary stent at time of surgery
- Blood loss during surgery
- Length of surgery (skin to skin, open to close?)
- Vascular reconstruction (arterial, venous) during surgery
- Closure technique
- Pancreatic leak risk score (when done? In record?)
- Surgical drains (what is needed)
- Post-op TPN

Variables with p-values less than 0.15 will be considered as potential candidates for a multivariable model. We will report odds ratios and 95% confidence interval. The area under the receiver operating characteristic (ROC) curve will be estimated as a measure of the ability of the model to discriminate between patients who had SSI within 90 days versus those who did not. An area under the ROC estimate of 0.7–0.8 will be regarded as acceptable, 0.8–0.9 will be regarded as excellent, and more than 0.9 will be regarded as outstanding.

We will also assess cost effectiveness of using ONT compared to SC. To achieve this, we will compare the cost to perform SC testing and ONT testing against costs associated with post-operative patient care. This will include the total cost to administer perioperative antibiotics, costs associated with length of hospital stay, and the costs associated with the need of additional procedures and tests associated with SSI (i.e. post-operative SC and antibiotic susceptibility testing, additional antibiotics, wound debridement, abdominal abscess drainage, CT scan, US scan).

For continuous variables, t-test will be performed and for binary variables chi-square or fisher's exact testing will be performed as appropriate. Additional analysis will be performed as necessary to determine differences in study arms. Should additional analysis beyond the scope of our abilities is necessary then a statistician will be employed.

Inpatient related costs associated with each intervention arm will be analyzed and compared with the assistance of the Robert D. and Patricia E. Kern Center for Science of Health Care in order to understand the economic impact of each intervention arm.

Handling of Missing Data

Missing data could arise from lost samples or from a catastrophic failure of computer storage and backup systems. If any of these were to occur before an intervention could be determined using ONT sequencing, we will note these events and revert the patient to Standard of Care group.

Primary Hypothesis:

The use of ONT sequencing, a novel metagenomic technique, will result in more rapid identification of organisms in intra-operatively collected bile samples and allow for earlier treatment of biliary microbial contamination. Supplementing SC with ONT sequencing data will allow patients to be treated earlier in the post-operative setting with tailored antibiotics, which will reduce the rate of biliary microbial contamination related SSIs in patients undergoing pancreatic head resection as compared to standard cultures alone and will improve antimicrobial stewardship by avoiding unnecessary use of antibiotics.

7 Safety and Adverse Events

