4.2 Method for Assigning Subjects to Treatment Groups

Two potential confounding variables exist in this patient population: operation type (pancreaticoduodenectomy vs total pancreatectomy) and pre-operative biliary stenting. Therefore, to eliminate potential bias between arms, patients will be stratified according to operation type (pancreaticoduodenectomy/total pancreatectomy) and biliary stenting (Y/N). Stratified patients will be assigned to arms by the study team using Medidata Rave with pre-determined assignments.

Given the prospective nature of this study, it will include subjects previously diagnosed with a specific disease and add newly diagnosed subjects in the future as patients are accrued.

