5.2 Sample Collection Visit

Following enrollment procedures, 2 cc of residual bile collected during surgery will be aliquoted into cryovial and placed on ice (not frozen). It will be picked up by the study team at the time of collection for ONT sequencing. Tissue Request Acquisition Group (TRAG) approval will be requested for managing of samples. The sample will be aliquoted from the clinical collection and so collection will not add additional time to the surgery procedure. Participants will be randomized in Medidata Rave to a study arm based on operation type and pre-operative biliary stenting using a dynamic stratification. Participants will be randomized in a 1:1 ratio.

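### The detection comparison that sizes the trial uses an unstratified test, and adjustment for stenting, a randomisation stratum that strongly predicts culture positivity, is not pre-specified

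*Combined protocol and SAP*

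**What the plan says.** - **Sizing (6.1).** The inputs are "Microbial detection positivity rate using standard cultures = 54" and "Microbial detection positivity rate using nanopore sequencing = 77" (both per cent), with "Power = 80%, alpha (type I error) = 0.05, beta (type II error) = 0.2". The result is "Sample size per group = 66 (total N = 132), Target size=70 per arm, total N=140".
- **Randomisation (4.2 and 5.2).** In 4.2, "patients will be stratified according to operation type (pancreaticoduodenectomy/total pancreatectomy) and biliary stenting (Y/N"); in 5.2, "Participants will be randomized in a 1:1 ratio".
- **Test (6.2).** In the paragraph on the primary analysis: "Comparisons of the proportions between the two study arms will be compared using" Fisher's exact or chi-square. Each proportion gets an exact 95% binomial interval. No interval is named for the difference in detection between arms, and no stratified test is named.
- **Adjustment (6.2).** There are two routes. Linear regression is used if baseline imbalances are seen. Separately, a list of candidate covariates for both primary and secondary analyses includes a biliary stent at surgery, with entry to a multivariable model screened at p < 0.15.
- **Pilot (1.4).** Biliary microbes were "detected in 54.7% (23/42) of patients undergoing total pancreatectomy or pancreaticoduodenectomy using SC techniques". Table 1 shows 22 patients with biliary instrumentation, all 22 of them positive.

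**The concern.** When randomisation balances the arms on a factor that strongly predicts the outcome, the difference between arms no longer varies with that factor. An unstratified test still counts the between-stratum variation as error. Its standard error is then too large, its type I error falls below the nominal level, and power is lost. The size of the loss depends on how strongly the factor predicts the outcome, and in the pilot the association is close to complete.

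Neither adjustment route settles the matter in advance. Stratifying on stenting is meant to prevent the imbalance that would trigger the first route. The second depends on a p-value screen, and the plan does not say that it replaces the named test of detection. At stake is the comparison to which the stated 80% power refers, particularly if sequencing adds less than the assumed 23 points.

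**Working it through.** **1. The plan's own figure.** Two-sided alpha of 0.05 is assumed, since the plan does not state sidedness. With pooled variance and no continuity correction:

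n = [1.96·√(2·0.655·0.345) + 0.8416·√(0.54·0.46 + 0.77·0.23)]² / 0.23² = (1.318 + 0.549)² / 0.0529 ≈ 66 per arm.

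This matches the plan. The same formula gives 82% power at 70 per arm. It contains no stratum.

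**2. Stratum rates.**
- Stented share: 22/42 = 0.524 (Table 1, with instrumentation standing in for stenting).
- Culture: 22/22 = 1.00 stented, (23 − 22)/(42 − 22) = 1/20 = 0.05 unstented.
- Sequencing, stented: 1.00, because 1.4 reports that it identified every contamination case.
- Sequencing, unstented: (0.77 − 0.524)/0.476 = 0.517. This is back-calculated from the 77%; the documents do not give it.

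**3. Standard error of the difference.** Variance times n per arm:
- Unstratified: p₁q₁ + p₂q₂ = 0.5476·0.4524 + 0.77·0.23 = 0.4248.
- Stratified: 0.524·(0 + 0) + 0.476·(0.05·0.95 + 0.517·0.483) = 0.1415.
- Ratio of standard errors: √(0.4248/0.1415) = 1.73. At 70 per arm the standard errors are 0.078 and 0.045.

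**4. Range.** The exact 95% lower limit for 22/22 is 0.85, and the upper limit for 1/20 is 0.25. Holding 54% and 77% fixed, with stented positivity from 0.85 to 1.00 and a stented share of 40% to 60%, the ratio runs from about 1.1 to 1.8.

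**5. Power by simulation.** 70 per arm, 37 stented and 33 unstented in each arm, two-sided 0.05. CMH is Cochran-Mantel-Haenszel stratified by stenting. Rates are stented/unstented.

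| Scenario | Culture | Sequencing | Chi-square | Fisher | CMH |
|---|---|---|---|---|---|
| Pilot values, 77% overall | 100/5% | 100/52% | 90% | 85% | 99.7% |
| Weaker link (assumed) | 90/14% | 95/57% | 88% | 84% | 96% |
| Weakest link (assumed) | 85/20% | 85/68% | 85% | 80% | 90% |
| Smaller yield (assumed) | 100/5% | 100/30% | 13% | 8% | 82% |

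In the last row the overall difference is (33/70)·(0.30 − 0.05) = 0.118, about 12 points.

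**6. Type I error with no difference.** At 100/5% in both arms, chi-square is about 0 and CMH about 3%. At 90/14% in both arms, chi-square is about 0.3% and CMH about 5%.

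**The case against.** The strongest reply is that the plan does not ignore stenting. It lists the stent as a candidate covariate for the primary analysis, and a factor this strong would almost certainly pass a p < 0.15 screen. That is fair: a reader might infer that stenting is left out altogether, and the documents do not support that. What remains is that adjustment is data-driven, that the screen leaves the named test of detection in place, and that a logistic model could fail to converge on a stratum in which everyone is positive.

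Further points that stand:
- **Power.** A reader might infer that the trial is underpowered for detection. At 54% versus 77%, the planned chi-square test exceeds the stated 80% in every scenario examined, and it errs on the conservative side.
- **Interval.** A reader might infer that a planned confidence interval is 1.7 times too wide. The plan defines none for this difference; the factor describes the standard error implied by an unstratified analysis.
- **Endpoint.** The declared primary endpoint is antibiotic administration, and the detection sentence falls under the subheading for descriptive statistics. No declared success criterion depends on this test.
- **Inputs.** The 1.7 comes from 42 patients, and instrumentation may not equal stenting. Section 1.1 also reports perfect agreement of sequencing with negative cultures, which conflicts with 77% against 54% and so with the 52% derived above. That conflict weakens the point value, but it also makes a yield below 23 points a realistic possibility, and there the choice of test matters most.

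**Conclusion.** The point holds as a matter of efficiency and pre-specification. The named test of detection does not use a stratum that the design already balances, and nothing in 6.2 commits to adjusting for it. At the assumed effect the cost is modest: about 90% power instead of over 99% at the pilot values, or 85% instead of 90% with the weakest stent link examined. It becomes serious if the true yield is smaller (13% against 82% in the assumed 30% scenario). The standard error is overstated by about 1.1 to 1.8 times, and 1.7 is only the pilot point value.

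These figures assume arms balanced on stenting, instrumentation standing in for stenting, and a two-sided test. The point does not show a false-positive risk, a breach of the stated power, or any effect on the antibiotic endpoint.

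**What to change.** In 6.2, replace the Fisher or chi-square test of detection with a Cochran-Mantel-Haenszel test stratified by stenting and operation type, the two factors in 4.2 and 5.2. Report the Mantel-Haenszel risk difference with its 95% confidence interval, and keep the exact per-arm intervals as description. State that this replaces covariate screening for the detection comparison.

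Name the two factors explicitly. The General Design section lists five stratification factors, adding age, sex and ASA score, so a reference to the randomisation strata would be ambiguous, and five factors in 140 patients would leave many sparse cells. The two lists should be reconciled.

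The cost is a sentence or two in the statistical section. Stenting and operation type are already recorded for randomisation, so no extra patients or data are needed.
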